### 14.2 Secondary Objectives

14.2.1 To determine whether the progression free survival at 1 year sMRI-guided, dose-escalated RT increases with newly-diagnosed GBMs. Subjects on this study will be followed for progression free survival (PFS) which is defined from the time of surgical resection to the time of either radiographic progression or death, whichever occurs first. While PFS actuarial curves will be assessed and compared to historical controls, we are particularly interested in comparing the 1-year PFS rate which, based on the control arm (receiving standard dose RT with TMZ) of recent GBM trials, is approximately 30% in historical cohorts [44-46].

### 14.3 Exploratory Objectives

14.3.1 To determine whether sMRI-guided, dose-escalated RT increases the overall survival of patients with newly-diagnosed GBMs. Subjects on this study will also be followed for overall survival (OS) which is defined from the time of surgical resection to the time of death. The OS actuarial curve and 1-year OS rate will be assessed and compared to historical controls. The 1-year OS rate of control arm patients on recent trials is approximately 66%

14.3.2 To determine whether sMRI data obtained after initiation of therapy (at 2 weeks after RT/TMZ start and prior to cycle 1 and 5 of adjuvant TMZ) will provide early evidence of GBM progression not seen on standard MRIs. Changes in sMRI parameters over time will be assessed to determine whether they will be able to predict development of recurrence. Global changes in sMRI parameters including to absolute metabolite concentrations or metabolic ratios will be examined to see if these factors may be an early marker of tumor recurrence. In addition, further assessments will be made on a voxel-wise basis to determine whether individual changes may be predictive of ultimate recurrence within particular voxels.

14.3.3 To determine whether performance on neurocognitive and quality-of-life (QOL) assessments in newly-diagnosed GBM patients treated with sMRI-guided, dose-escalated RT differ from historical controls. We will compare performance on neurocognitive and QOL assessments in our 30 subject cohort with performance by historical control cohorts from recent GBM trials (eg. RTOG 0525 and 0825) [45, 46]. Better performance may be attributable to better control of disease while worse performance may imply increased toxicity from the study treatment regimen.

**14.3 Accrual rate and numbers:** The anticipated rate of accrual will be 2-3 patients/month among three sites. This will allow consenting of 30 patients over a period of 1.5 years.

**14.3 Criteria for removal from trial:** All reasons for discontinuation of treatment must be documented.

**14.3.1** Progression of disease will be hard to determine due to pseudoprogression as defined in section 11.3. The final progression free survival will be determined at year 1, which is beyond pseudoprogression possibility.

**14.3.2** Patient may withdraw from study at any time for any reason.

**14.4 Adverse event stopping rule:** Safety assessments will be performed throughout treatment, at two week intervals during RT and prior to each odd number adjuvant TMZ cycle following completion of RT. Toxicity will be carefully assessed using CTCAE v4.03 criteria, and the rate of radiation necrosis development will be determined. While we expect this regimen to be tolerated based on the previous experience reported by Tsien et al. [9], we will still employ an interim safety analysis with a special stopping rule if neurotoxicity is greater than expected. Because the expected incidence of late grade 3+ neurotoxicity with standard-of-care chemoradiation is ~5%, or 2 of 30 patients in our planned cohort, we will employ the following interim analysis and stopping rule after 10 subjects have completed treatment and have been followed for 6 months after completion of chemoradiation: if more than 2 subjects (out of 10) develop CTCAE v4.03 grade III or greater neurotoxicity (> 20% incidence) judged to be at least possibly due to RT by 6 months from completion of RT/TMZ, study accrual will halt and await assessment of toxicities by the DSMC to review attribution of toxicities before a decision will be made about either permanent closure or re-opening with continuation/completion of study accrual.

**14.5 Statistical analysis for survival endpoints:** The primary objectives are to determine the feasibility of this escalated protocol and the safety of increased doses in patients with GBM. We anticipate that 30 patients will provide us sufficient data to make these conclusions. Since survival analyses are exploratory objectives of this study, these endpoints are not used to determine accrual numbers for this study. The PFS of patients in this protocol will be compared with historical controls, and that data will be used to estimate the effect size for future power analyses. With a planned accrual of 30 subjects, the following power to detect potential improvements in 1 year PFS is as follows: 1-year PFS rate is expected to be 30-35% based on historical controls [44-46]. Our study will have 82% power to detect an improvement to a rate of 60% at  $\alpha=0.05$  using a two-sided test. Cox's proportional hazard regression model will be applied to model 1-year PFS outcome to test whether subjects treated with escalated RT doses guided by the sMRI demonstrate significantly higher PFS as compared to historical controls receiving standard treatment, controlling for other potential risk factors. Of note, calculations to determine the power to detect a certain PFS effect size based the number of patients we needed to determine feasibility and safety were presented above. However, this study was not actually powered based on PFS improvement.

**14.6 Statistical analysis of sMRI scans:** This study is mainly using pre-RT sMRI parameters to help define a region at high risk for recurrence that can be treated with higher doses of RT. Exploratory objectives will involve examining changes in absolute metabolite levels and metabolic ratios during RT that may be useful for adaptive radiation therapy (changing dose plan during early phase of RT). sMRI data will be evaluated both on a patient-wise basis and on a voxel-wise basis with utilization of deformable registration technique, as needed, to achieve good matching of maps across serially acquired scans.

**14.7 Statistical analysis of neurocognitive function and QOL scores:** Linear mixed effects models will be applied to model the repeatedly measured score from each assessment and/or test over time. We hypothesize that changes in individual and/or composite metabolite levels will be predictive of the temporal changing patterns in the scores on the neurocognitive functional tests and QOL assessments. Changes in individual and multiple metabolite levels

within normal brain surrounding the region of the tumor as well as in tumor-bearing regions of brain will be evaluated with scores on these assessments using logistic regression models.

**14.8 Interim analysis and stopping rule for efficacy/futility:** While there will be stopping rules for toxicity/adverse events (see **Section 14.4**), there will not be stopping rules for efficacy/futility. The primary goal of the study is to determine the feasibility and safety of sMRI-guided, dose-escalated RT and TMZ for newly diagnosed GBM patients. At the time we anticipate performing interim analysis for toxicity assessment in the first 10 patients with adequate follow-up, approximately 20 patients will have already initiated therapy allowing up to 10 patients to avoid enrollment if this treatment regimen is determined to be too toxic.

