### Late Delayed

Possible late delayed effects of radiotherapy include radiation necrosis, leukoencephalopathy, endocrine dysfunction, and radiation-induced neoplasms. In addition, neurocognitive deficits, which could lead to mental slowing and behavioral change, are possible. Permanent hearing impairment and visual damage are rare. Cataracts can be encountered.

**4.2 Risks associated with temozolomide (standard care).** The risks related to the use of temozolomide are outlined in the information below regarding this drug.

**4.3 Risks associated with sMRI (research-related).** The risks of undergoing sMRIs are the same as those with conventional MRI. Movement or heating of metallic implants is a potential risk, and so subjects will be screened to exclude people with metallic implants, fragments, or pacemakers. Some individuals experience claustrophobic reactions in the scanner. Subjects will be informed of this prior to the study, but because it is difficult to predict who will have such a reaction, this is not a specific exclusion criterion. Any subject experiencing claustrophobia or discomfort during the study will be removed from the scanner immediately. There is no invasive component to this study and so discomfort, bruising, or infection is not a risk. Of note, there is NO injection of contrast agent.

There may be additional risks associated with scanning at 3T, which are addressed here:

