Blood/bone marrow	Grade 2 - ANC<1500-1000 or PLTS<100,000-50,000	Continue RT but omit TMZ until ANC≥1500 and PLTS≥100,000, ↓TMZ dose by 15%.
	Grade 3 - ANC<1000-500 or PLTS<50,000-25,000	Continue RT but omit TMZ until ANC≥1500 and PLTS≥100,000, ↓TMZ dose by 25%.
	Grade 4 - ANC<500 or PLTS<25,000	Hold RT and TMZ. Resume RT when ANC ≥500 & PLTS≥25,000 and TMZ when ANC≥ 1500 & PLTS≥100,000, ↓TMZ dose by 50%.
Gastrointestinal	Grade 2 - Nausea/vomiting on optimal anti-emetics	TMZ may be held until recovery to grade 0-1 at physician's discretion.
	Grade 3 - Nausea/vomiting on optimal anti-emetics	Omit TMZ until grade 0-2 (or ≤1 grade of baseline), ↓TMZ dose by 25%.
	Grade 4 - Nausea/vomiting on optimal anti-emetics	Omit TMZ until grade 0-2 (or ≤1 grade of baseline), ↓TMZ dose by 50%.
Non-hematologic Other	Grade 2	TMZ may be held until recovery to grade 0-1, ↓TMZ dose by 15% at physician's discretion.
	Grade 3	Omit TMZ until grade 0-2 (or ≤1 grade of starting value for pre-existing abnormalities), ↓TMZ dose by 25%.
	Grade 4	Omit TMZ until grade 0-2 (or ≤1 grade of starting value for pre-existing abnormalities), ↓TMZ dose by 50%.
Development of alopecia does not require dose modification		

**9.3 Adjuvant treatment:** If the attribution of the adverse event can be clearly linked to TMZ, these dose modifications should be followed.

During adjuvant therapy only, patients who require resection for radiation necrosis without evidence of recurrent tumor may continue to receive protocol therapy as long as they are not off study drug for >6 consecutive weeks.

**9.3.1 Dose modification criteria for adjuvant TMZ after RT (cycles 1-12):** Adjuvant TMZ dose for cycle 1 is 150 mg/m^2 given days 1-5 of 28 day cycle. This dose is used even if TMZ dose reductions or treatment delays were necessary during concurrent RT/TMZ

as long as other criteria at time of starting cycle 1 do not preclude beginning adjuvant TMZ therapy. If tolerated, subsequent cycles will increase dose to 200 mg/m^2 given days 1-5 of 28 day cycles. Maximum dose reduction is 50% of the starting dose (75 mg/m^2 if dose reduction required after cycle 1 or 100 mg/m^2 if dose reduction required after cycle 2 or later). If significant toxicity is still experienced at 50% of the starting dose, TMZ will be discontinued.

Use Common Terminology Criteria for Adverse Events (CTCAE) v4.0 unless otherwise specified		

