## 11.3 Response criteria

**11.3.1 Measurable Disease:** Measurable lesions with clearly defined margins by contrast-enhanced MRI scan beyond pseudoprogression period. We anticipate an extended period of pseudoprogression with dose escalation.

**11.3.2 Objective Status, To Be Recorded at Each Evaluation:** Unless progression is observed, objective status can only be determined when ALL measurable sites and lesions are assessed.

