### 11.3.3 Response Definitions

**11.3.3.1 Complete Response (CR):** Complete disappearance of all measurable disease in contrast-enhancing MRI. No new lesions. No evidence of non-evaluable disease. All measurable lesions and sites must be assessed using the same techniques as baseline. Patients must be on no steroids.

**11.3.3.2 Partial Response (PR):** (Measurable disease only) Greater than or equal to 50% decrease under baseline in tumor volume [43] of all measurable lesions. No progression of evaluable disease. No new lesions. All measurable lesions and sites must be assessed using the same techniques as baseline. *The steroid dose at the time of the scan evaluation should be no greater than the maximum dose used in the first 8 weeks from initiation of therapy.*

**11.3.3.3 Stable Disease (SD):** Does not qualify for CR, PR, or progression. The designation of SD requires a minimum of 8 weeks duration (2 assessment of stable disease 8 weeks apart). All measurable sites must be assessed using the same techniques as baseline. The steroid dose at the time of the scan evaluation should be no greater than the maximum dose used in the first 8 weeks from initiation of therapy.

**11.3.3.4 Progressive Disease (PD):** 50% increase in the tumor volume of all measurable lesions over previous exam (over baseline if no decrease) using the same techniques as baseline, OR clear appearance of any new lesion/site, OR clear clinical worsening or failure to return for evaluation due to death or deteriorating condition (unless clearly unrelated to this cancer). NOTE: Increasing contrast enhancing disease in months 1-3 (potentially up to month 6) post-RT may represent pseudoprogression. For the current study, we anticipate that incidence of this phenomenon will be increased.

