Because of difficulties in the interpretation of pseudo-progression on MRI, the first three post-RT/TMZ scans should NOT be used to declare progression. Progressive worsening on subsequent imaging studies usually distinguishes true progression from pseudoprogression. In particular, DSC perfusion imaging may be helpful at distinguishing true and pseudoprogression. If the rCBV map does not show evidence of increased perfusion in regions with increasing contrast-enhanced lesion(s), then pseudoprogression is favored and patient may be maintained on study. Subsequent increases up to 6 months post-RT will be evaluated on a case-by-case at a multi-disciplinary tumor board of the respective institution to assist in making a determination regarding true versus pseudoprogression and whether pathologic sampling would be beneficial. The date of progression will be backdated to when the changes were first observed in the case that the patient is later determined to have true progression.

**11.3.3.5 Regressive Disease (REGR):** (Evaluable disease only) Unequivocal reduction in extent of contrast as compared to baseline-enhancement or a decrease in mass effect as agreed upon independently by primary physician and quality control physicians; no new lesions.

**11.3.3.6 Unknown:** Progression has not been documented and one or more measurable sites have not been assessed.

**11.4 Best Response:** This will be calculated from the sequence of objective statuses. For patients with all disease sites assessed every evaluation period, the best response will be defined as the best objective status as measured according to section 11.5.

**11.5 Neurological Exam:** Although not used for determining response, it is useful to evaluate improvement in the neurologic exam, as compared with the baseline assessment, that should coincide with objective measurement of tumor size.

NEURO EXAM STATUS (compared to pre-treatment exam)	
Better	Must be on stable or decreasing dose of steroids
Same	Failure to qualify for better or worse
Worse	Include patients requiring increasing steroid doses to remain stable

**11.6 Performance Status:** Patients will be graded according to Karnofsky Performance Status (see Appendix 3).

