## 15.0 DATA COLLECTION

**15.1 Data submission forms:** A copy of the eligibility/registration form will be completed and kept at the Emory Winship Cancer Institute Clinical Research Office.

- The clinical management system being used for this study is The Online Collaborative Research Environment (OnCore). OnCore will be used to record all study related information for all registered patients. All data must be entered no later than 30 days following each visit completion. All queries are to be resolved within 4 weeks of issue.

**15.2 Imaging and RT data:** Imaging data will be collected with masked patient identification. All diagnostic imaging data sets will be electronically transferred under the study ID to a secure server at Emory University. In addition, patient treatment plans, including isodose clouds and all structure including tumor volumes and OARs under the study ID, will be similarly transferred and stored. For instructions on how to transfer each data set, please contact [name] at [contact].

**15.3 REDCap data:** To be able to accurately determine/analyze the progression (date and recurrence patterns) and outcomes/benefits of the new treatment strategy, we need the following information uploaded to the REDCap database set up for this trial. Our REDCap for this study is set up under Study ID, rather than patients' identity. The following documents will be collected to REDCap after masking patient's name or hospital ID number. Those include all reports from neuro-oncologists (to monitor the condition of the patients and any new interventions that are prescribed to the patients) and pathology reports that are generated after surgical interventions. The initial pathology report has genomic/histological information of the tumor subtype while the follow up pathology reports contain the tumor/necrosis proportion of sampling to determine progression/treatment effect. For instructions on how to upload data to the REDCap, please contact [name] at [contact].

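### Tumour-board adjudication of treatment effect stops at 6 months post-RT, so late radiation necrosis can be scored as a 1-year PFS failure

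*Combined protocol and SAP*

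**What the plan says.** - **Progression rule (11.3.3.4).** The imaging limb is "50% increase in the tumor volume of all measurable lesions over previous exam", with a new lesion or clear clinical worsening as alternatives. This rule carries no time limit and does not mention radiation necrosis.
- **Safeguards in the same section.** The first three scans after RT/TMZ may not be used to declare progression. After that, "Subsequent increases up to 6 months post-RT will be evaluated on a case-by-case at a multi-disciplinary tumor board". An rCBV map without raised perfusion favours pseudoprogression; no end date is given for this.
- **PFS definitions.** Section 11.9 runs from surgery or biopsy to progression under 11.3.3.4 or death, with confirmation on later scans and backdating to the first date. Section 14.2.1 runs from resection to radiographic progression or death.
- **Assumption about year 1 (14.3.1, criteria for removal).** "The final progression free survival will be determined at year 1, which is beyond pseudoprogression possibility".
- **Expected treatment effect.** Section 11.3.1: "We anticipate an extended period of pseudoprogression with dose escalation". Section 4.1, late delayed effects: "Possible late delayed effects of radiotherapy include radiation necrosis". Section 14.4 plans to determine the rate of radiation necrosis.
- **Where necrosis is separated from tumour.** Section 9.3, on adjuvant treatment: "patients who require resection for radiation necrosis without evidence of recurrent tumor may continue to receive protocol therapy". Section 15.3, on data collection: "the follow up pathology reports contain the tumor/necrosis proportion of sampling to determine progression/treatment effect".

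**The concern.** Section 14.3.1 treats the 1-year reading as free of treatment effect, and the only explicit adjudication step ends at 6 months post-RT. Yet the protocol expects pseudoprogression to last longer under this regimen and names necrosis as a late effect. A patient whose enhancing volume grows by 50% because of necrosis at, say, month 8 post-RT meets the imaging limb of 11.3.3.4. The same patient, if resected and found free of tumour, is treated under 9.3 as not having recurred. The plan does not say which reading governs PFS.

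At stake is the 1-year PFS rate, in which 14.2.1 states a particular interest. It is compared with historical controls given standard-dose RT, and 14.5 uses the result to estimate effect size for future power calculations. A scoring error would therefore carry into the next trial.

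**Working it through.** **1. The plan's own figure.** Inputs from 14.5: n=30, historical 1-year PFS 30-35%, target 60%, two-sided alpha 0.05, stated power 82%. One-sample normal approximation at p0=0.35:

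- SE under the null = sqrt(0.35×0.65/30) = 0.0871; SE under the alternative = sqrt(0.60×0.40/30) = 0.0894.
- Power = Φ((0.25 − 1.96×0.0871)/0.0894) = Φ(0.887) = 81.2%. With the null SE throughout, Φ(0.25/0.0871 − 1.96) = 81.9%.

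The stated 82% reproduces at a historical rate of 35%. At 30% the first formula gives 93.6%.

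**2. Where year 1 falls relative to RT.** RT must start within 50 days of resection (8.1.1). Assumptions: earliest start day 21; 30 weekday fractions span about 39 days; 4 to 6 week break (8.2); 28-day cycles; MRI before each odd cycle (7.1); adjuvant TMZ still running at cycle 9.

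| | RT starts day 21 | RT starts day 50 |
|---|---|---|
| RT ends | day 60 | day 89 |
| Day 365, months post-RT | (365−60)/30.44 = 10.0 | (365−89)/30.44 = 9.1 |
| 6-month review limit | day 243 | day 272 |
| Limit to day 365 | 122 days = 4.0 months | 93 days = 3.1 months |

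The three barred scans (before cycles 1, 3 and 5) fall at about 0.9-1.4, 2.8-3.2 and 4.6-5.1 months post-RT. The scans before cycles 7 and 9 fall at about 6.4-6.9 and 8.3-8.7 months, after the review limit and before day 365. The number of cycles is at the physician's discretion, so the scan count is approximate.

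**3. Do the open-ended provisions close the gap?**

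- rCBV (11.3.3.4) makes pseudoprogression favoured and allows the patient to stay on study. It does not say the growth is not a PFS event.
- Confirmation (11.9) asks for later scans. Sections 1.0 and 11.3.3.4 take continued worsening as the mark of true progression, so a treatment effect that went on enlarging would satisfy it.
- Pathology (15.3) is collected for the right purpose, but neither PFS definition refers to it.
- Section 9.3 governs continuation of therapy, not endpoint scoring.

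**4. Illustration of size.** The documents give no rate of late necrosis read as progression, so 5, 10 and 15 percentage points (1.5, 3 and 4.5 of 30 patients) are assumed. Exact binomial, n=30, rejecting at the smallest count with upper-tail probability at most 0.025: ≥15/30 against 30% (tail 0.0169) and ≥17/30 against 35% (tail 0.0124). Power is P(X ≥ cut-off) at the observed rate.

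| Points misread | Observed PFS | Power against 30% | Power against 35% |
|---|---|---|---|
| 0 | 60% | 90% | 71.5% |
| 5 | 55% | 77% | 50% |
| 10 | 50% | 57% | 29% |
| 15 | 45% | 36% | 14% |

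The table assumes that every misread patient would otherwise be progression-free at 1 year and that the historical rates contain no such misreading. The exact test is stricter than the normal approximation, which is why its 35% baseline is below 82%. As a cross-check on the normal approximation, misreading 10% of the true successes (60% to 54%) takes power from 81% to 58% at 35%, and from 94% to 80% at 30%.

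**The case against.** The strongest reply is that the plan is not silent. The rCBV clause, the confirmation wording in 11.9 and the pathology purpose in 15.3 have no cut-off, and 9.3 shows that resected necrosis without tumour is not handled as recurrence. This stands against the reading that all late enhancing growth is automatically progression with no exception: the documents support only that late necrosis *can* be scored so.

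The protocol also describes pseudoprogression as an early effect, usually within 3 months and potentially up to month 6. On that description the year-1 sentence is not self-contradictory. But it does not cover necrosis, which is listed separately, and it sits poorly with the extended period expected in 11.3.1.

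Three further inferences are tempting and unsupported:

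- **That clinical worsening from necrosis is necessarily a PFS event.** It is under 11.9 through 11.3.3.4, but not under 14.2.1.
- **That the formal toxicity thresholds are under-counted.** Both the 30-patient criterion (14.1.2) and the 10-patient stopping rule (14.4) close at 6 months after RT/TMZ, so a later event lies outside them whatever it is called.
- **That PFS is shown to be biased against the regimen overall.** Barring the first three scans may favour the study arm over controls assessed by other rules, partly offset by backdating.

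The one dose-specific figure given, no late grade III or greater CNS toxicity up to 75 Gy in the cited dose-escalation series (1.0), points to a small problem. It concerns graded toxicity, however, not imaging change. Finally, PFS is secondary (called exploratory in 14.5), did not size the trial, and is to be analysed with a Cox model rather than the test used for illustration here.

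**Conclusion.** The gap is real but narrower than a reader might infer. Explicit adjudication ends at 6 months post-RT, about 3 to 4 months before the 1-year reading, and no rule says how treatment effect without tumour is scored in that interval. This can bias 1-year PFS downward. The timing rests on the assumed RT start of day 21 to 50 and RT duration of 39 days. The power losses rest on assumed misreading rates and show only that a few patients in 30 matter; they do not estimate what will happen. The net direction of bias against historical controls remains open. The point does not touch the primary objectives, but it should be settled before the PFS result is compared with history or used to plan a further trial.

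**What to change.** These changes concern endpoint scoring only, not treatment decisions.

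1. In 14.3.1 (criteria for removal), delete the closing clause that places year 1 past any pseudoprogression.
2. In 11.3.3.4 and 11.9, extend the existing tumour-board, rCBV and pathology review to all changes first seen up to the 1-year PFS read. Because dates are backdated, include changes whose confirming evidence arrives after that date.
3. State that growth shown by pathology to be treatment effect without tumour is not a PFS event, and count it in the necrosis rate of 14.4.
4. Reconcile 11.9 with 14.2.1 on whether clinical worsening is a PFS event.
5. Report 1-year PFS twice, with unresolved late cases counted as progression and as treatment effect.

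The cost is endpoint wording, some additional late reviews and one sensitivity analysis; the review process and the pathology reports already exist. The downside is that some late events will stay indeterminate, which the two-way report makes visible.

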#### **13.2 Winship Cancer Institute Data Safety Monitoring Committee:**

The study will also be followed by the Winship Cancer Institute Data Safety Monitoring Committee to allow for local review and confirmation of proper study execution and safety measures.

**13.2.1** Patient safety, study efficacy and compliance will be reviewed at the Neuro-oncology Working Group meeting. The Data and Safety Monitoring Committee (DSMC) of the

Winship Cancer Institute will also oversee the conduct of this study (annually or semi-annually – depending on the risk level assigned to the protocol by the Winship Cancer Institute Clinical and Translational Research Committee). The DSMC will review pertinent aspects of study conduct including patient safety, compliance with protocol, data collection and efficacy. The committee will review the charts of 10% of patients enrolled to the study and two of the first 5 patients entered to the study. The Committee reserves the right to conduct additional audits if necessary. The clinical Principal Investigator (PI) at each site or his designee is responsible for notifying the DSMC about the accrual of patients when the first 5 have been entered to the study. The PI or designee will also notify the DSMC of study status within 2 months before the next scheduled review is due.

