## 14.0 STATISTICAL CONSIDERATIONS AND METHODOLOGY

### 14.1 Primary Objectives

14.1.1 To determine the feasibility of using sMRI to guide dose-escalated RT for newly-diagnosed GBMs. Feasibility of this approach will be determined by whether treatment volumes based on sMRI can be co-registered with clinical images and transferred into the radiation treatment execution platform in a seamless manner, so that sMRI information can be efficiently applied to the patient treatment.

14.1.2 To determine the safety of using sMRI to guide dose-escalated RT for newly-diagnosed GBMs. The safety of this approach will be confirmed by assessing toxicity potentially attributable to the dose-escalated RT. Toxicity will be determined by CTCAE v4.0 criteria. If > 6 of 30 patients (> 20% of subjects) experience a grade 3 or greater toxicity by 6 months after completion of RT/TMZ that is ruled as at least possibly attributable to the dose-escalated RT, then the safety of this treatment approach will be questioned and require further review by the study team. Interim analyses with stopping rules are described later in this Section.

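### The accrual halt in Section 14.4 is tested only once, after 10 subjects have 6 months of follow-up, so a third qualifying event that already settles the rule does not stop enrolment

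*Combined protocol and SAP*

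**What the plan says.** Section 14.4 sets the adverse event stopping rule. The count is of subjects with CTCAE grade 3 or worse neurotoxicity judged at least possibly due to RT by 6 months after RT/TMZ, and the limit is more than 2 of 10. The halt is a "stopping rule after 10 subjects have completed treatment and have been followed for 6 months after completion of chemoradiation". If the limit is passed, "study accrual will halt and await assessment of toxicities by the DSMC", and the study then closes or re-opens. The rule is motivated by a background figure: "expected incidence of late grade 3+ neurotoxicity with standard-of-care chemoradiation is ~5%, or 2 of 30 patients".

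Section 14.8 describes the same single look, in the first 10 patients with adequate follow-up. It states that by then "approximately 20 patients will have already initiated therapy", so that up to 10 could avoid enrolment.

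Other safety review is planned without a numerical trigger:
- Section 14.4: safety assessments every two weeks during RT, then before odd-numbered adjuvant cycles.
- Section 13.2.2: monthly review of observed toxicities, and rapid SAE reporting.
- Section 13.3: monthly teleconferences across the sites.
- Section 13.2.1: DSMC oversight "annually or semi-annually".

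The only other count is in Section 14.1.2, and it covers toxicity judged at least possibly due to the escalated RT: "If > 6 of 30 patients (> 20% of subjects) experience a grade 3 or greater toxicity by 6 months after completion of RT/TMZ". The stated consequence is: "then the safety of this treatment approach will be questioned and require further review by the study team". No accrual halt is attached to it.

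**The concern.** The criterion is a count that can only rise. Once three of the 10 interim subjects have a qualifying event, the limit is passed whatever happens to the other seven. Waiting for the tenth subject's 6-month visit adds nothing to that decision. As written, the halt still waits for that visit, and patients keep starting escalated RT meanwhile.

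The plan already collects what is needed to see the third event, through two-weekly assessments during RT and monthly reviews. What is missing is a rule that links that information to the halt. Safety is one of the two primary objectives (Section 2.1), and the stated purpose of the look is to spare patients enrolment if the regimen proves too toxic. The delay works against that purpose.

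**Working it through.** **Inputs from the documents.** Look after 10 subjects with 6 months of follow-up, limit more than 2 of 10 (14.4). Chemoradiation about 42 days, or 42/30.44 = 1.38 months (8.2). Planned accrual 30. Rate 2-3 a month (Accrual rate and numbers, Section 14); the same paragraph gives 30 patients in 1.5 years, i.e. 30/18 = 1.67 a month. Section 3.1 gives 1 a month per site, i.e. 3 a month over three sites.

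**Assumptions, because the documents give no figure.** Even accrual, with patient k starting at k/r months for rate r; each patient has a qualifying event with probability p; event timing as set out below.

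**Step 1: the plan's own figure of about 20.** Time of look T = 10/r + 1.38 + 6. Patients started by then = r × T, rounded down and capped at 30.

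| r per month | T (months) | r × T | Started by the look | Left to spare |
|---|---|---|---|---|
| 1.67 | 13.4 | 22.3 | 22 | 8 |
| 2 | 12.4 | 24.8 | 24 | 6 |
| 2.5 | 11.4 | 28.4 | 28 | 2 |
| 3 | 10.7 | 32.1 | 30 (cap) | 0 |

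The figure is nearly reproduced at 1.67 a month. Exactly 20 needs 10 + 7.38r = 20, so r = 1.36. At the stated 2-3 a month it is 24-30, so the look spares 0-6 of the planned 30 rather than up to 10.

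**Step 2: how often the rule trips.** P(3 or more of 10) = 1 − Σ C(10,x) p^x (1−p)^(10−x), x = 0 to 2.
- p = 5%: 1 − (0.599 + 0.315 + 0.075) = 1.2%
- p = 20%: 32%
- p = 30%: 1 − (0.028 + 0.121 + 0.233) = 62%
- p = 40%: 83%

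Acting at the third event leaves these unchanged, because the same sets of outcomes among the same 10 subjects trip the rule. Only the date moves.

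**Step 3: patients who start between the third event and the look, in trials that breach.** Simulation, at least 20,000 trials per cell, accrual capped at 30. Three onset patterns: uniform from RT start to 6 months after RT; late (uniform over months 3-6 after RT); early (uniform from RT start to 1 month after RT). Mean extra patients:

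| p | r | Late | Uniform | Early |
|---|---|---|---|---|
| 30% | 1.67 | 5.6 | 8.7 | 13.5 |
| 30% | 2 | 5.6 | 9.3 | 15.0 |
| 30% | 2.5 | 6.6 | 11.0 | 18.4 |
| 30% | 3 | 5.6 | 10.7 | 19.8 |
| 40% | 1.67 | 6.3 | 9.6 | 14.1 |
| 40% | 2 | 6.3 | 10.3 | 15.7 |
| 40% | 2.5 | 7.3 | 12.2 | 19.1 |
| 40% | 3 | 6.3 | 12.0 | 20.5 |

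That is about 5-7, 9-12 and 14-20 patients. At 2-3 a month with uniform onset, the third event comes on average 4.1-4.8 months before the look (p = 30%) or 4.6-5.3 months before it (p = 40%).

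**The case against.** **The single look is disclosed.** Section 14.8 openly accepts that many patients will have started by then. That stands as a description of intent, but the number accepted, about 20, does not follow from the stated accrual rate, and the plan gives no reason to wait once the count is settled.

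**Other oversight exists.** A reader might infer that several severe events early in the trial would provoke no response. The documents do not support that. Toxicities are reviewed monthly, problem sessions can be held up to weekly, SAEs are reported rapidly, and the DSMC receives SAE summaries and could act. The accurate statement is that no pre-specified rule halts accrual.

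**Onset may be late.** The rule is motivated by late neurotoxicity, and Section 4.1 lists necrosis as a late delayed effect. If so, the late column applies and the figure is about 5-7, not 9-12. This stands, which is why the range is shown. At the plan's 5% background rate the rule trips in only 1.2% of trials.

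**Which ten?** Section 14.4 counts subjects who completed treatment and follow-up; Section 14.8 refers to the first 10 with adequate follow-up. Someone who stops early or dies could be in one set and not another. This also stands: a third event settles the rule only once the cohort is fixed.

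**A larger fix is tempting.** A reader might infer that accrual should also halt at a seventh event under Section 14.1.2, as a cost-free parallel change. It is not parallel. Exceeding 6 of 30 there prompts a study-team review; it is not called a failure and carries no halt today. It also counts any grade 3 or worse toxicity, not only neurotoxicity. Seven or more of 30 occurs with probability 39% at a 20% rate and 84% at 30%. A halt there would be a new stopping rule on a broader endpoint and would need its own operating characteristics.

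**Conclusion.** The point holds for Section 14.4. The halt is tied to one look although a third event among the interim subjects decides it earlier, and no other pre-specified rule closes the gap. The cost of waiting, when the rule will be breached, is about 9-12 further patients started on escalated RT with uniform onset, about 5-7 with late onset and about 14-20 with early onset. These figures rest on true rates of 30-40%, even accrual of 1.67-3 a month, a cap of 30 patients, and onset patterns that the documents do not give. The direction does not depend on them: in every setting examined, the third event comes before the look and patients start in between. Separately, the figure of about 20 in Section 14.8 fits roughly 1.4-1.7 a month, not the stated 2-3. The point does not extend to a halt under Section 14.1.2, nor to a claim that safety goes unwatched.

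**What to change.** In Section 14.4, state that accrual halts and the case goes to the DSMC as soon as the third qualifying event occurs among the subjects of the 10-subject interim cohort. Keep the more-than-2-of-10 threshold and the existing 6-month look. Define the cohort once, for example as the first 10 to start protocol RT, say how a member who stops early or dies before 6 months is counted, and use the same definition in Section 14.8. Keep the running three-site count at the monthly teleconference already planned in Section 13.3. When Section 14.8 is edited, bring the number already on therapy into line with the accrual rate the plan intends.

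The cost is one added sentence, the cohort definition and a running count. For the same 10 subjects the probability of halting is unchanged, so there are no extra false alarms; the downside is an earlier pause in trials that would pause anyway. No dose, treatment or patient-management rule is affected.
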